7.2 PARTICIPANT DISCONTINUATION/WITHDRAWAL FROM STUDY

When study intervention is discontinued, participants should have an end of treatment/discontinuation assessment and continue follow-up assessments until radiographic progression or the start of subsequent therapy, whichever comes first, as outlined in the SOAs (see [Section 1.3](#)). In addition, ad hoc scans, as part of standard of care, will be collected for participants who have discontinued treatment for reasons other than radiographic progression and prior to any alternate therapies. Information on survival follow-up and new anticancer therapy will be collected for all participants via telephone calls, participant medical records, and/or clinic visits, until any of the following occurs:

- Death
- Lost to follow-up
- Study termination by the Sponsor
- Participant requests to be withdrawn from follow-up
- Investigator requests that the participant is withdrawn from follow-up

If a participant requests to be withdrawn from the study, the request must be documented in the source documents and signed by the Investigator. The primary reason for withdrawal from study should be documented on the appropriate eCRF page. If the participant withdraws from study, the Sponsor may retain and continue to use any data collected before such withdrawal of consent. In addition, the study staff may use a public information source (eg, county records) to obtain information about survival status only. However, participants who withdraw consent will not be followed for any reason after consent has been withdrawn. Participants who receive study intervention and subsequently withdraw from the study will not be replaced.

7.3 LOST TO FOLLOW-UP

A participant will be considered lost to follow-up if he or she repeatedly fails to return for scheduled visits and is unable to be contacted by the study site.

The following actions must be taken if a participant fails to return to the clinic for a required study visit:

- The site must attempt to contact the participant and reschedule the missed visit as soon as possible and counsel the participant on the importance of maintaining the assigned visit schedule and ascertain whether or not the participant wishes to and/or should continue in the study.
- Before a participant is deemed lost to follow-up, the Investigator or designee will make every effort to regain contact with the participant (where possible, 3 telephone calls and, if necessary, a certified letter to the participant's last known mailing address or local equivalent methods). These contact attempts should be documented in the participant's medical record or study file.
- Should the participant continue to be unreachable, he/she will be considered to have withdrawn from the study.

8 STUDY ASSESSMENTS AND PROCEDURES

Please see [Section 1.3](#) for the SOAs to be performed during the study. All activities must be performed and documented for each participant in the order of SOAs. Participants will be closely monitored for safety and tolerability throughout the study. Participants should be assessed for toxicity prior to each dose; dosing will occur only if the clinical assessment and local laboratory test values are acceptable as deemed by the PI.

If the timing of a protocol-mandated study visit coincides with a holiday, weekend, or other administrative disruption that precludes the visit, the visit should be scheduled on the nearest following feasible date. The time between doses must not be less than minus 3 days from the normal schedule of the last dose received (doses must not be administered < 25 days for a Q4W schedule or < 18 days apart for a Q3W).

Collection of any non-safety-related data or participant samples may be terminated by the Sponsor at any time if further collection of such data or samples is also not related to the study's primary or secondary objective. The decision to discontinue any data collection will be communicated to the sites and Institutional Review Board (IRB)/Independent Ethics Committee (IEC) by means of a memorandum and will not require a protocol amendment.

8.1 EFFICACY ASSESSMENTS

Participants will undergo tumor assessments as designated in the SOAs (see [Section 1.3](#)) regardless of dose delays, until loss of clinical benefit as determined by the Investigator (unless the participant withdraws consent or the Sponsor terminates the study). All participants who discontinue study intervention for reasons other than radiographic progression (eg, AEs) will continue tumor assessments until death, disease progression, initiation of another systemic anticancer therapy, loss to follow-up, withdrawal of consent, or study termination, whichever occurs first. At the Investigator's discretion, tumor assessments may be repeated at any time if PD is suspected.

Measurable and evaluable lesions should be assessed and documented at screening. Tumor assessments performed as standard of care prior to obtaining informed consent and within 28 days prior to treatment do not have to be repeated at screening.

Screening assessments must include computed tomography (CT) scans (with IV contrast unless contraindicated and oral contrast as appropriate per institutional standards). A spiral CT scan of the chest may be obtained but is not a requirement. If a CT scan with contrast is contraindicated (ie, in participants with contrast allergy or impaired renal clearance), a non-contrast CT scan of the chest may be performed and magnetic resonance imaging (MRI) scans of the abdomen, pelvis, and head (as applicable) should be performed as applicable.

If a CT scan for a tumor assessment is performed in a positron emission tomography (PET)/CT scanner, the CT acquisition must be consistent with the standards for a full contrast diagnostic CT scan.

Bone scans (technetium-99m [TC-99m]) or sodium fluoride (NaF) PET should be performed at screening if clinically indicated. If bone metastases are present at screening and cannot be seen on CT or MRI scans, or if clinically indicated, TC-99m and NaF-PET bone scans should be repeated when complete response (CR) is identified in target disease or when progression in bone is suspected.

CT scans of the head, neck, or extremities should also be performed if clinically indicated and repeated throughout the study if there is evidence of disease at screening.

All measurable and evaluable lesions should be re-assessed at each subsequent tumor evaluation. The same radiographic procedures used to assess disease sites at screening should be used for subsequent tumor assessments (eg, same contrast protocol for CT scans).

Response will be assessed by the Investigator using RECIST v1.1 (see [Appendix 3](#)).

Assessments should be performed by the same evaluator, if possible, to ensure internal consistency across visits. Results must be reviewed by the Investigator before dosing at the next cycle.

8.1.1 Laboratory Assessments of Tumor Markers

Results for tumor markers (eg, CA19-9, PSA, etc) will be collected if performed as part of standard of care.

PSA is required for participants in the prostate cohorts under Amendment 3+ (see [Table 3](#) and [Table 4](#)).

8.2 SAFETY ASSESSMENTS

Safety assessments will consist of monitoring and recording AEs, including SAEs, performing protocol-specified safety laboratory assessments, measuring protocol specify vital signs, and conducting other protocol-specified tests that are deemed critical to the safety evaluation of the study. Planned timing for all safety assessments is provided in the SOAs ([Section 1.3](#)).

Certain types of events require immediate reporting to the Sponsor, as described in [Section 8.3.1.1](#).

8.2.1 Medical History and Demographic Data

Medical history, including clinically significant diseases, surgeries, cancer history (including stage, date of diagnoses, and prior cancer therapies and procedures), reproductive status, smoking history, use of alcohol, and drugs of abuse, will be recorded at baseline. In addition, all medications (eg, prescription drugs, over-the-counter drugs, vaccines, herbal or homeopathic remedies, nutritional supplements) used by the participant within 28 days prior to study intervention will be recorded. Demographic data may include age, sex, and race/ethnicity.

8.2.2 Physical Examinations

A complete physical examination should be performed at screening and should include an evaluation of the head, eyes, ears, nose, and throat, and the cardiovascular, dermatological, musculoskeletal, respiratory, gastrointestinal, genitourinary, and neurological systems. Any abnormality identified at baseline should be recorded on the Medical History eCRF page.

ECOG Performance Status (see [Appendix 2](#)) should be assessed per the SOAs in [Section 1.3](#).

At subsequent visits (or as clinically indicated), limited, symptom-directed physical examinations should be performed. Changes from baseline abnormalities should be recorded in participant notes. New or worsened clinically significant abnormalities should be recorded as AEs on the Adverse Event eCRF page.

8.2.3 Vital Signs

Vital signs should include measurements of respiratory rate, pulse rate, systolic and diastolic blood pressure, pulse oximetry (only at baseline), and temperature as outlined in the SOA ([Section 1.3](#)). Vital signs collected at the screening visit should be recorded on the eCRF. For

each visit thereafter, only vital signs obtained prior to the first drug infusion on Day 1 or during an AE (eg, temperature or event of fever) should be recorded on the eCRF. All vital signs collected per protocol should be documented in the participant's medical record.

Vital signs should be measured on Day 1 of every cycle prior to administration of study intervention. Vital signs may be measured, if medically indicated, at other time points.

Vital signs should be measured within 0-20 minutes prior to the first infusion and, if clinically indicated, during or after the infusions (see [Section 6](#)).

8.2.4 Electrocardiograms

A single ECG recording will be obtained at Baseline, as outlined in the SOAs ([Section 1.3](#)), and may be obtained at unscheduled time points as indicated.

All ECG recordings must be performed using an institutionally approved ECG. Lead placement should be as consistent as possible. ECG recordings must be performed after the participant has been resting in a supine position for at least 10 minutes. All ECGs are to be obtained prior to other procedures scheduled at that same time (eg, vital sign measurements, blood draws) and should not be obtained within 3 hours after any meal. Circumstances that may induce changes in heart rate, including environmental distractions (eg, television, radio, conversation), should be avoided during the pre-ECG resting period and during ECG recording.

For safety monitoring purposes, the Investigator must review, sign, and date all ECG tracings. Paper copies of ECG tracings will be kept as part of the participant's permanent study file at the site. The following should be recorded on the appropriate eCRF page: heart rate, RR interval, QRS interval, PR duration, uncorrected QT interval, and QTcF based on the machine readings of the individual ECG tracings. Any morphologic waveform changes or other ECG abnormalities must be documented on the eCRF page.

8.2.5 Clinical Safety Laboratory Assessments

Clinical laboratory tests will be performed at the local institution as described in the SOAs ([Section 1.3](#)).

The Investigator must review the laboratory report, document this review, and record any clinically relevant changes occurring during the study on the appropriate eCRF. The laboratory reports must be filed with the source documents. Clinically significant abnormal laboratory findings are those that are not associated with the underlying disease, unless judged by the Investigator to be more severe than expected for the participant's condition.

In the event of a Grade 3 or Grade 4 laboratory toxicity, the test for the abnormal laboratory value should be repeated until the event is resolved to \geq Grade 1 or baseline.

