5.1 INCLUSION CRITERIA

Participants are eligible to be included in the study only if all the following criteria apply:

General Inclusion Criteria

1. Participant must be ≥ 18 years of age inclusive, at the time of signing the informed consent.
2. Male or female participants of child-producing potential must agree to use contraception (as detailed in [Appendix 6](#)) or avoidance of pregnancy measures during the study and for 7 and 5 months, respectively, after the last dose.
3. Females of childbearing potential must have a negative serum or urine pregnancy test.

Cancer-specific Inclusion Criteria

4. Histologically or cytologically confirmed cancer that is metastatic, unresectable, or recurrent. Under Amendment 2 only, enrollment will be limited to tumor types known to be responsive to immunotherapy, have high prevalence (> 20%) of CD8 > 15% tumors, and/or have been observed in the study to have tumors transition from CD8 low to CD8 high following initiation of immunotherapy.
 - a. Participants with these tumor types will be eligible to participate regardless of screening CD8 results (either $\geq 15\%$ or $< 15\%$).
 - b. Tumor types for investigation under Amendment 2:
 - i. Melanoma, Gastric, Small cell lung cancer, NSCLC, HCC, Cutaneous squamous cell carcinoma, RCC, Cervical, Gastroesophageal junction cancer, Urothelial bladder cancer, Sarcoma (soft tissue only), Neuroendocrine, SCCHN, Ovarian, Gynecologic malignancies, Merkel Cell, Prostate, Microsatellite instability high Colorectal, Anal (squamous cell only)
5. Participants who have received prior immunotherapy, including prior anti-PD-1 or anti-PD-L1 therapies, will be allowed to participate in this study.
 - a. Participants who received prior anti-PD-1 or anti-PD-L1 may participate only if their prior anti-PD-1 or anti-PD-L1 monotherapy or combination therapy were NOT the last treatment prior to participation on this study.
 - b. Participants who had prior immunotherapies and experienced Grade 1-2 immune-related adverse event (irAE) must have documentation that their irAEs are \leq Grade 1 or baseline using current Common Terminology Criteria for Adverse Events v5.0 (CTCAE v5.0) **and** participants must be off steroid therapy and/or other immunosuppressive therapy, as treatment for irAEs, for ≥ 14 days from Cycle 1, Day 1.

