 - c. Participants who experienced Grade 3 irAEs consisting of laboratory abnormalities that were asymptomatic and have now resolved to \leq Grade 1 or baseline **and** participants who have been off steroid and/or other immunosuppressive therapy, as treatment for irAEs, for ≥ 30 days from Cycle 1, Day 1.
6. Concurrent malignancies are permitted if any one of the following applies:
 - a. Previously treated malignancy for which all treatment of that malignancy was completed at least 2 years before enrollment and no evidence of disease exists, or
 - b. With agreement from the Sponsor and Principal Investigator (PI), participants who have a concurrent malignancy that is clinically stable and does not require tumor-directed treatment are eligible to participate if the risk of the prior malignancy interfering with either safety or efficacy endpoints is very low, or
 - c. With agreement from the Sponsor and PI, other malignancies may be permitted if the risk of the prior malignancy interfering with either safety or efficacy endpoints is very low.

7. Provide newly obtained core needle or incisional biopsy of a non-bone tumor lesion not previously irradiated. Fine needle aspiration is not acceptable.
 - a. Biopsies should be obtained from sites that do not pose significant risk to the participant based on the tumor site and the procedure used. Biopsy sites/procedures including, but not limited to, the brain, open lung/mediastinum, pancreas, or endoscopic procedures extending beyond the esophagus, stomach, or bowel would be considered to pose a significant risk to the participant. Procedures to areas that are deemed by the Investigator to be of non-significant risk based on individual clinical scenarios will be permitted.
8. Measurable disease as defined by RECIST v1.1.
 - a. With the exception of prostate cancer participants enrolled under Amendment 3+ who must have measurable disease, participants who do not have measurable disease by RECIST criteria but whose disease can be objectively measured through tumor markers or another disease-specific standard are considered eligible.
9. Eastern Cooperative Oncology Group (ECOG) performance status of 0 or 1.
10. Aspartate aminotransferase (AST) and alanine aminotransferase (ALT) ≤ 3 x upper limit of normal (ULN).
 - a. Participants with hepatocellular carcinoma (HCC) may be eligible provided they have AST and ALT that are ≤ 5.0 x ULN.
11. Hemoglobin ≥ 9 g/dL.
12. Total bilirubin $\leq 1.5 \times$ ULN.

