5.2 EXCLUSION CRITERIA

Participants are excluded from the study if any of the following criteria apply:

General Exclusion Criteria

1. Participants who had a medical condition that required a surgical procedure and were subject to general anesthesia within 4 weeks prior to beginning protocol therapy are excluded except the use of general anesthesia during biopsy procedures, indicated for patient comfort and or safety will be permitted.
2. Pregnant or breastfeeding.
3. Significant gastrointestinal disorder(s) (eg, active Crohn's disease or ulcerative colitis or a history of extensive gastric resection and/or small intestinal resection).
4. Has interstitial lung disease or active, noninfectious pneumonitis.
5. Has a transplanted organ or has undergone allogeneic bone marrow transplant.
6. Has received a live vaccine within 30 days prior to first dose.
7. Known hypersensitivity to a component of protocol therapy.
 - a. Participants with known hypersensitivity to ipilimumab and/or nivolumab are excluded.
8. Uncontrolled concurrent illness including, but not limited to, ongoing or active infection, clinically significant non-healing or healing wounds, symptomatic congestive heart failure, unstable angina pectoris, cardiac arrhythmia, significant pulmonary disease (shortness of breath at rest or on mild exertion), uncontrolled infection, or psychiatric

illness/social situations that, in the opinion of the investigator, would pose a safety concern or limit compliance with study requirements.

Cancer-specific Exclusion Criteria

9. Participants who experienced any \geq Grade 3 symptomatic irAE on a prior immunotherapy study will be excluded from this study regardless of resolution of the irAE.
10. Any known, untreated, brain metastases. Treated participants must be stable 4 weeks after completion of treatment for brain metastases, and image-documented stability is required. Participants must have no clinical symptoms from brain metastases and have not required systemic corticosteroids > 10 mg/day prednisone or equivalent for ≥ 2 weeks prior to first dose of study intervention.
11. Participants with an active, known or suspected autoimmune disease. Participants with type I diabetes mellitus, hypothyroidism only requiring hormone replacement, skin disorders (such as vitiligo, psoriasis, or alopecia) not requiring systemic treatment, or conditions not expected to recur in the absence of an external trigger are permitted to enroll.

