AEs associated with nivolumab with or without ipilimumab exposure may represent an immunologic etiology. These irAEs may occur shortly after the first dose or several months after the last dose of treatment and may affect more than one body system simultaneously. Therefore, early recognition and initiation of treatment is critical to reduce complications. Based on existing clinical study data, drug-related AEs have included pulmonary toxicity, renal toxicity (including acute renal failure), endocrine abnormalities, gastrointestinal toxicity, dermatologic toxicity (including rash), and hepatotoxicity. For nivolumab monotherapy and combination therapy, the majority of these AEs have been managed successfully with supportive care and, in more severe cases, a combination of dose delay, permanent discontinuation, and/or use of corticosteroids or HRT (endocrinopathies). For suspected irAEs, ensure adequate evaluation to confirm etiology or exclude other causes. Additional procedures or tests such as bronchoscopy, endoscopy, and skin biopsy may be included as part of the evaluation.

For Amendments 1 and 2, dose modification and toxicity management guidelines for irAEs associated with nivolumab with or without ipilimumab are provided in [Table 7](#). For Amendment 3+ (advanced prostate cohorts), requirements for the discontinuation of study treatment for irAEs associated with nivolumab with or without ipilimumab are provided in [Table 9](#).

Table 7: Dose Modification and Toxicity Management Guidelines for Adverse Events Associated with Nivolumab with or without Ipilimumab

Drug-Related Adverse Event (AE) per CTCAE V5	Severity	Action Taken	Clarifications, Exceptions, and Resume Criteria
Gastrointestinal			
Colitis or Diarrhea	Grade 2	Delay dose	Dosing may resume when AE resolves to baseline
	Grade 3	Nivolumab monotherapy: Delay dose	Dosing may resume when AE resolves to baseline
		When administered with ipilimumab: Permanently Discontinue Ipilimumab	Nivolumab monotherapy may be resumed when AE resolves to baseline. If Grade 3 diarrhea or colitis recurs while on nivolumab monotherapy, permanently discontinue
	Grade 4	Permanently discontinue	
Renal			
Serum Creatinine Increased	Grade 2 or 3	Delay dose	Dosing may resume when AE resolves to Grade \leq 1 or baseline value
	Grade 4	Permanently discontinue	
Pulmonary			
Pneumonitis	Grade 2	Delay dose	Dosing may resume after pneumonitis has resolved to \leq Grade 1.
	Grade 3 or 4	Permanently discontinue	

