Drug-Related Adverse Event (AE) per CTCAE V5	Severity	Action Taken	Clarifications, Exceptions, and Resume Criteria
Hepatic			
Aspartate aminotransferase (AST), alanine aminotransferase (ALT), or total bilirubin (T.bili) increased	AST or ALT > 3x and ≤ 5 x upper limit of normal (ULN) or T.Bili >1.5x and ≤ 3 x ULN, regardless of baseline value	Delay dose	Dosing may resume when laboratory values return to baseline.
	AST or ALT > 5 x ULN or T. bili > 3 x ULN, regardless of baseline value	Delay dose or Permanently discontinue	In most cases of AST or ALT > 5 x ULN, study treatment will be permanently discontinued. If the investigator determines a possible favorable benefit/risk ratio that warrants continuation of study treatment, a discussion between the investigator and the Medical Monitor/ designee must occur and a written agreement from Medical Monitor prior to resuming therapy.
	Concurrent AST or ALT > 3 x ULN and T.bili > 2 x ULN, regardless of baseline value	Permanently discontinue	
Endocrinopathy			
Adrenal Insufficiency	Grade 2 adrenal insufficiency	Delay dose	Dosing may resume with lab confirmation of hormone replacement treatment.
	Grade 3 or 4 adrenal insufficiency or adrenal crisis	Delay dose or permanently discontinue	Mandatory discussion with and approval from the Medical Monitor needed prior to resuming therapy. If adrenal insufficiency resolves or is adequately controlled with physiologic hormone replacement, participant may not require discontinuation of study drug.
Hyperglycemia	Hyperglycemia requiring initiation or change in daily management (Grade 2 or 3)	Delay dose	Dosing may resume if hyperglycemia resolves to Grade ≤ 1 or baseline value, or is adequately controlled with glucose-controlling agents.
	Grade 4	Delay dose or permanently discontinue	Mandatory discussion with and approval from the Medical Monitor needed prior to resuming therapy. If hyperglycemia resolves, or is adequately controlled with glucose-controlling agents, participant may not require discontinuation of study drug.

Drug-Related Adverse Event (AE) per CTCAE V5	Severity	Action Taken	Clarifications, Exceptions, and Resume Criteria
Hypophysitis/Hypopituitarism	Symptomatic Grade 1-3 that is also associated with corresponding abnormal lab and/or pituitary scan	Delay dose	Dosing may resume if endocrinopathy resolves to be asymptomatic, or is adequately controlled with only physiologic hormone replacement.

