Other Clinical AE			
Pancreatitis: Amylase or Lipase increased	Grade 3 with symptoms	Delay dose	Note: Grade 3 increased amylase or lipase without signs or symptoms of pancreatitis does not require dose delay. Dosing may resume when patient becomes asymptomatic.
	Grade 4	Permanently discontinue	
Uveitis	Grade 2 uveitis	Delay dose	Dosing may resume if uveitis responds to topical therapy (eye drops) and after uveitis resolves to Grade \leq 1 or baseline. If patient requires oral steroids for uveitis, then permanently discontinue study drug.
	Grade 3 or 4 uveitis	Permanently discontinue	

Drug-Related Adverse Event (AE) per CTCAE V5	Severity	Action Taken	Clarifications, Exceptions, and Resume Criteria
Other Drug-Related AE (not listed above)	Grade 2 non-skin AE, except fatigue	Delay dose	Dosing may resume when AE resolves to Grade ≤ 1 or baseline value.
	Grade 3 AE - First occurrence lasting ≤ 7 days	Delay dose	Dosing may resume when AE resolves to Grade ≤ 1 or baseline value.
	Grade 3 AE- First occurrence lasting > 7 days	Permanently discontinue	
	Recurrence of Grade 3 AE of any duration	Permanently discontinue	
	Grade 4 or Life-threatening adverse reaction	Permanently discontinue	
Other Lab abnormalities			
Other Drug-Related lab abnormality (not listed above)	Grade 3	Delay dose	Exceptions: No delay required for: Grade 3 lymphopenia Permanent Discontinuation for: Grade 3 thrombocytopenia > 7 days or associated with bleeding.
	Grade 4	Permanently discontinue	Exceptions: The following events do not require discontinuation of study drug: 
 • Grade 4 neutropenia ≤ 7 days • Grade 4 lymphopenia or leukopenia • Grade 4 isolated electrolyte imbalances/abnormalities that are not associated with clinical sequelae and are responding to supplementation/appropriate management within 72 hours of their onset
Infusion Reactions (manifested by fever, chills, rigors, headache, rash, pruritus, arthralgia, hypotension, hypertension, bronchospasm, or other allergic-like reactions.)			
Hypersensitivity reaction or infusion reaction	Grade 3 or 4	Permanently discontinue	Refer to Section 6.6.1.2 on Treatment of Related Infusion Reactions

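### The Section 8.2.5 retest rule has its inequality reversed, so a Grade 3 or 4 laboratory value already meets the point at which retesting may stop

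*Protocol*

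**What the plan says.** The last sentence of Protocol Section 8.2.5 is triggered by a laboratory toxicity of Grade 3 or Grade 4. It says the abnormal test "should be repeated until the event is resolved to \geq Grade 1 or baseline". It gives no retest interval and no other stopping condition.

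Elsewhere the protocol sets recovery levels in these places:

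- Section 5.1, criterion 5b, for prior Grade 1-2 immune-related events: "documentation that their irAEs are \leq Grade 1 or baseline".
- Section 5.1, criterion 5c, for prior Grade 3 events: "laboratory abnormalities that were asymptomatic and have now resolved to \leq Grade 1 or baseline".
- Section 6.6.1.1, Table 7, serum creatinine: "Dosing may resume when AE resolves to Grade \leq 1 or baseline value". The row for other drug-related adverse events sets the same level, as does the hyperglycemia row (which also accepts adequate control). The pneumonitis and uveitis rows also use Grade 1 or lower. Footnote b to the table allows treatment to resume at Grade 0 or 1.
- Table 7, lower level of AST, ALT or bilirubin elevation: "Dosing may resume when laboratory values return to baseline". Colitis and diarrhea also require return to baseline.

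The Table 7 row for other drug-related laboratory abnormalities gives no recovery grade. The SAP does not restate the Section 8.2.5 rule.

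**The concern.** The word *resolved* and the symbol ≥ contradict each other. On a scale where a higher grade is worse, an event resolves by falling to a grade or below it. As printed, the end point takes in every abnormal grade, including the two that start the rule, so a site that never repeats the test has complied with the text.

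This is an operative safety instruction, and Section 10.1.7 has monitors verify conduct against the approved protocol. At stake is whether severe laboratory abnormalities are followed until they recover. No estimate or decision rule in the statistical plan is affected.

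**Working it through.** No statistical figure is involved, so the check is one of logic, followed by a look at what else in the protocol covers the gap.

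**1. Which grades meet the end point.** Section 10.5.3 defines severity from Grade 1 (mild) upward. Grade 0 means no abnormality, as in Table 7 footnote b. Leaving aside the *or baseline* alternative:

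| Grade | Meets ≥ 1 (as printed) | Meets ≤ 1 |
|---|---|---|
| 0 | no | yes |
| 1 | yes | yes |
| 2 | yes | no |
| 3 (trigger) | yes | no |
| 4 (trigger) | yes | no |

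As printed, 2 of 2 trigger grades meet the end point at onset. With ≤, 0 of 2 do. As printed, a fully normal result (Grade 0) qualifies only through the baseline alternative.

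**2. Comparison with the other recovery levels.** Criterion 5c is the closest in wording and subject, since it concerns Grade 3 laboratory abnormalities that have recovered, and it uses ≤. Criterion 5b, the Table 7 rows that name Grade 1, and footnote b agree with it. The remaining recovery rows for colitis, diarrhea and liver tests are stricter. None supports ≥ Grade 1. These are eligibility and dose-resumption rules rather than the retest rule itself, so they show the protocol's convention and do not override the sentence.

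**3. What already limits the harm.**

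- *Scheduled tests (Section 1.3, Tables 1-4).* Cycle 1 Day 8 to the next scheduled test is 22 − 8 = 14 days. After that the spacing is 21 days on 3-week dosing and 28 days on 4-week dosing, each visit ±3 days.
- *After treatment.* End of treatment falls 15-30 days after the last dose and first follow-up at 90 days, so the gap is 90 − 30 = 60 to 90 − 15 = 75 days. With the ±7-day windows it is 83 − 37 = 46 to 97 − 8 = 89 days. Under footnote b of the schedule tables, that visit becomes a telephone contact if other therapy has started.
- *Dosing.* Section 8 requires laboratory values acceptable to the investigator before each dose, but names no grade.
- *Adverse events.* Section 8.3.2 follows events to resolution, and Section 10.5.3 calls for supplemental tests when medically indicated.

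**4. What is left uncovered.** The adverse-event safeguards apply only if the abnormality counts as an adverse event. That requires clinical significance in the investigator's judgment (Section 10.5.1.1) or another criterion in Section 10.5.5: symptoms, a change in study treatment, or a medical intervention. Some Grade 3 or 4 values need meet none of these. Table 7 states that "Grade 3 increased amylase or lipase without signs or symptoms of pancreatitis does not require dose delay". It requires no delay for Grade 3 lymphopenia and no discontinuation for Grade 4 lymphopenia. In the prostate cohorts, Table 9 exempts most Grade 3 laboratory abnormalities from discontinuation. For such values, Section 8.2.5 is the only text that sets a recovery level for retesting.

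**The case against.** The strongest objection is that the point rests on a single symbol in text machine-read from a PDF, and that text contains character-level misreads. The steady-state subscripts in Section 4.3.1 change from letters to digits, and Table 3 gives cfDNA as ctDNA in one row. This is a fair reason to check the source. However, these are letter and digit confusions, not swapped inequality signs. The same text carries ≤ correctly in Sections 5.1 and 6.6.1.1, and ≥ correctly in Section 5.2 ("Participants who experienced any \geq Grade 3 symptomatic irAE"). A misread is unlikely but not excluded.

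A second objection is that no one would be misled, because *resolved* makes the intent plain and the literal reading leaves the rule with no effect. The intent is indeed plain, which is why the correction is certain. It does not make the printed instruction right.

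Third, the residual harm is close to nil. Section 8.2.5 sets no retest interval, so routine cycle testing could satisfy even the corrected rule during treatment. Most Grade 3 or 4 drug-related abnormalities lead to a delay or discontinuation under Table 7, which makes them adverse events. Appendix 4 (Section 10.4) also allows extra tests at any time. Most of this stands and keeps the point small. But a permission to test is not a requirement, and none of these provisions supplies a recovery level for the values described in step 4.

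**Conclusion.** The concern holds. As printed, the retest rule is met at onset by both grades that trigger it, and nothing in the protocol or SAP corrects it. It should be fixed because it is a wrong safety instruction with an unambiguous correction. The consequence is minor: it is largely confined to Grade 3 or 4 values that prompt no treatment change and are not judged adverse events, and it is most relevant after treatment, when scheduled tests are farthest apart. Those visit gaps describe the existing schedule; correcting the symbol does not change them. No sample size, stopping boundary, endpoint or analysis is affected. The conclusion assumes that the symbol in the source PDF is the one shown in the extracted text.

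**What to change.** Check the symbol against the source PDF. If it reads ≥, amend the end of the sentence in Section 8.2.5 so that testing is repeated until the event has resolved to ≤ Grade 1 or baseline. Leave the stricter Table 7 requirements in force for resuming dosing, namely return to baseline for colitis, diarrhea and the liver tests. The cost is one character in the protocol, which can go into the next amendment. It needs no new visits or analyses and no change to the SAP.
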